6.5 POOLING OF CENTRES

This section is not applicable, because the trial was performed in only one centre.

6.6 HANDLING OF MISSING DATA AND OUTLIERS

Handling of missing data and outliers will be performed as described in the CTP, Section 7.5.

Missing or incomplete AE dates are imputed according to BI standards (see BI-KMED-BDS-HTG-0035) (3).

Missing data and outliers of PK data are handled according to BI standards (see BI-KMED-TMCP-MAN-0012 (4) and BI-KMED-TMCP-MAN-0014 (5)).

ECG and ECG-PK analysis

If single cardiac cycles of an ECG (out of the generally four) are missing, the arithmetic mean for this single ECG will be computed with the reduced (1, 2 or 3) number of cardiac cycles.

If replicate ECG recordings are missing, the arithmetic means per time point will be computed with the reduced number (1 or 2) of recordings.

For the classification of the on-treatment QTc/QT intervals into “no new onset” / “new onset” categories, the handling of missing values is described in Additional [Section 10.1.3](#).

For subjects on active drug (e.g. post dose time points), missing plasma concentration values with ‘BLQ’ in the comment field will be replaced by $\frac{1}{2}$ LLOQ for the exposure-response analysis. For placebo subjects, the missing plasma concentration values will be replaced by 0 for the exposure-response analyses.

6.7 BASELINE, TIME WINDOWS AND CALCULATED VISITS

The baseline value is defined as the last measurement before administration of trial medication (BI 706321 or Placebo).

Section 6.1 of the CTP:

Study measurements and assessments scheduled to occur ‘before’ trial medication administration on Day 1 are to be performed and completed within a 3 h-period prior to the trial drug administration (including blank values for PK).

The acceptable deviation from the scheduled time for vital signs, ECG, and laboratory tests will be ± 15 min for the first 4 h after trial drug administration, ± 30 min thereafter on Day 1, ± 60 min on Day 2 (except for urinalysis which can be performed between wake-up time to the scheduled time), and ± 120 min from 48 h post administration onwards.

The tolerance for drug administration will be ± 1 min on Days 1, 12, 19 and ± 10 min on all other treatment days.

The tolerance for PK blood sampling will be ± 5 minutes for up to 6 hours (including) after dosing, 15 minutes for time points from more than 8 hours to 12 hours after dosing, 60 minutes for time points from more than 24 hours to 48 hours after dosing, and 120 minutes for time points at 72 hours or later after dosing.

Adherence to time windows will be checked via the consistency check listings at the RPM.

Unscheduled measurements of laboratory and vital signs data will be assumed to be repeat measurements of the most recent scheduled measurement (e.g. for follow-up or confirmation of a particular value). Therefore, unscheduled measurements will be assigned to the planned time point of the previous scheduled measurement.

There will be a centralised evaluation of the 12-lead ECG recordings at the time points and for the ECG recordings specified in [Table 6.7: 1](#) for Part I.

At screening and end of trial examination, single ECGs will be recorded and will not be transferred to the central ECG lab.

Section 5.2.4.1 of the CTP: *Central ECG lab evaluation will be performed for all time points with triplicate ECGs. For some time points (...) three triplicate ECGs are recorded (i.e. on days 1 and 19 in Part I and on day 1 in Part II). Always, only the first single ECG per triplicate will be evaluated.*

The baseline value of an ECG variable is defined as the mean of the ECG variable values prior to drug administration.

For the exposure response analyses, pairs of ECG variables and corresponding plasma concentrations will be built using the same planned time points, e.g., the HR change from baseline and the plasma concentration measured at planned time 1:00 will build one pair. Whether a time deviation between PK blood sampling time and corresponding ECG recording is too big and the pair has to be excluded from the analysis will be decided no later than at the RPM. Data exclusion due to time deviations will only be applied to subjects on active study treatment. The acceptable maximum time deviations between ECG recordings and plasma concentration sampling are proposed to be

- 30 minutes for up to (and including) 12 hours after dosing,
- 60 minutes for time points from 24 hours up to (and including) 36 hours after dosing,
- 90 minutes for time points at 48 hours or later after dosing,

Pairs with time deviations exceeding those specified above will be excluded from exposure-response analyses. When the sampling time of the blood sample or the ECG recording is not available, the pair will also be excluded.

Table 6.7: 1 Time schedule of 12-lead ECG recordings in Part I

Visit	Day	Planned time [hh:mm] (relative to drug administration)	Study phase	Central evaluation
1	-28 to -1		Screening	NA
2	1	-01:30	Baseline	First single ECG of each triplicate
		-01:15		
		-01:00		
		01:00		
		02:00		
		04:00		
		08:00		
		12:00		
	2	24:00		
		36:00		
3	3	48:00		
	5	96:00	On treatment	NA
	6	120:00		
	7	144:00		
	9	192:00		
	11	240:00		
	13	288:00		
	15	336:00		
	17	384:00		
19	19	431:15	On treatment	First single ECG of each triplicate
		431:30		
		431:45		
		433:00		
		434:00		
		436:00		
		440:00		
		444:00		
	20	456:00		
	21	480:00		
22	22	504:00	On treatment	NA
	24	552:00		
3	27	624:00	End of trial examination	

7. PLANNED ANALYSIS

If not stated otherwise, the trial parts will be evaluated separately.

Safety analysis (refer to [Section 7.8](#)) will be performed by [REDACTED] and will be presented in Sections 15.1 to 15.4 of the CTR and in Appendix 16.2 and 16.1.13.1.

Statistical model-based analysis of PK will be performed by [REDACTED] and will be presented in Section 15.5 of the CTR and Appendix 16.1.13.3.

Descriptive data analysis of PK will be performed by the department [REDACTED] [REDACTED] at [REDACTED] The results will be presented in Section 15.6 of the CTR and Appendix 16.1.13.5.

The format of the listings and tables will follow the BI standards (see BI-KMED-BDS-HTG-0045 (6)) with the exception of those generated for PK-calculations following BI standards for PK/PD analysis (7).

The individual values of all subjects will be listed, sorted by treatment group, subject number and visit. The listings will be included in Appendix 16.2 of the CTR.

No statistical interim analysis is planned.

For end-of-text tables, the set of summary statistics for non-PK parameters is:

N	number non-missing observations
Mean	arithmetic mean
SD	standard deviation
Min	minimum
Median	median
Max	maximum

For analyte concentrations and PK parameters, the following descriptive statistics will additionally be calculated:

Nobs	number of observations
CV	arithmetic coefficient of variation
gMean	geometric mean
gCV	geometric coefficient of variation
P10	10th percentile
Q1	1st quartile
Q3	3rd quartile
P90	90th percentile

The data format for descriptive statistics of concentrations will be identical to the data format of the respective concentrations. The descriptive statistics of PK parameters will be calculated using the individual values with the number of decimal places as provided by the evaluation program. Then the individual values as well as the descriptive statistics will be reported with three significant digits in the CTR.

Tabulations of frequencies for categorical data will include all possible categories available in the CRF and will display the number of observations in a category, as well as the percentage (%). Percentages will be rounded to one decimal place and will be based on all subjects in the respective subject set whether they have non-missing values or not. The category 'missing' will be displayed only if there are actually missing values.

Units of variables should be given in the titles or column/row descriptors in brackets (e.g. (mg)).

Exclusion of PK parameters

The ADS “ADPP” (PK parameters) contains column variables APEX and APEXC indicating inclusion/exclusion (APEX) of a PK parameter and an analysis flag comment (APEXC). All analyses based on the PKS or ECGPCS, respectively, will include parameters only if they are not flagged for exclusion, that is APEX is equal to “Included”.

Exclusion of PK concentrations

The ADS “ADPC” (PK concentrations per time-point or per time-interval) contains column variables ACEX and ACEXC indicating inclusion/exclusion (ACEX) of a concentration and an analysis flag comment ACEXC. Exclusion of a concentration depends on the analysis flag comment ACEXC. For example, if ACEXC is set to ‘ALL CALC’, the value will be excluded for all types of analyses based on concentrations. If ACEXC is set to ‘DESC STATS’ the value will be excluded from descriptive evaluations per planned time point/time interval. If ACEXC contains the addition ‘TIME VIOLATION’ or ‘TIME DEVIATION’ the value can be used for further analyses based on actual times. If ACEXC is set to ‘HALF LIFE’, the value will be excluded from half-life calculation (and, as a consequence, any calculation that relies on λ_z) only; the value is included for all other analyses.

Further details are given in *BI-KMED-TMCP-MAN-0014* “Noncompartmental Pharmacokinetic / Pharmacodynamic Analyses of Clinical Studies” (5) and *BI-KMED-TMCP-MAN-0010*: “Description of Analytical Transfer Files and PK/PD Data Files” (8).

7.1 DEMOGRAPHIC AND OTHER BASELINE CHARACTERISTICS

Only descriptive statistics are planned for this section of the report, based on the TS. The data will be summarised by treatment group and in total.

7.2 CONCOMITANT DISEASES AND MEDICATION

Frequency tables are planned for this section of the report, based on the TS.

Concomitant diseases will be coded using the coding system of the Medical Dictionary for Drug Regulatory Activities (MedDRA). Medications will be coded using the World Health

Organization Drug Dictionary (WHO-DD). The coding version number will be displayed as a footnote in the respective output.

The diagnoses and medications will be listed. Subjects without any concomitant diagnoses or concomitant therapies will be marked with a “No” in the respective column.

The relevance of the concomitant therapies to the evaluation of PK will be decided no later than at the RPM.

7.3 TREATMENT COMPLIANCE

Section 4.3 of the CTP: *Compliance will be assured by administration of all trial medication in the study centre under supervision of the investigating physician or a designee. The measured plasma concentrations and/or urinary excretion of trial medication will provide additional confirmation of compliance.*

It is not intended to list the compliance separately. Any deviations from complete intake will be addressed in the RPM (cf. TSAP [Section 6.2](#)) and described in the CTR.

7.4 PRIMARY ENDPOINT

Refer to TSAP [Section 7.8](#) for a description of the analysis of the primary endpoint.

7.5 SECONDARY ENDPOINTS

7.5.1 Key secondary endpoint

[figure not shown]
This section is not applicable as no key secondary endpoint has been specified in the protocol.

[figure not shown]
[figure not shown]
7.5.2 (Other) Secondary endpoints

[figure not shown]
Section 7.3.2 of the CTP:

[figure not shown]
Primary analyses

[figure not shown]
The secondary endpoints (refer to [Section 5.2.2](#)) will be analysed descriptively. Analyses will be performed for BI 706321.

7.7 EXTENT OF EXPOSURE

Descriptive statistics are planned for this section of the report based on the TS. The date and time of drug administration will be listed for each subject.

7.8 SAFETY ANALYSIS

All safety analyses will be performed on the TS except for the exposure-response analyses, which are based on the ECGPCS.

The safety data for treated subjects who failed to complete the study (dropouts or withdrawals) will be reported as far as their data are available. All withdrawals will be documented and the reason for withdrawal recorded.

7.8.1 Adverse Events

AEs will be coded using MedDRA. The coding version number will be displayed as a footnote in the respective output.

Unless otherwise specified, the analyses of AEs will be descriptive in nature. All analyses of AEs will be based on the number of subjects with AEs and NOT on the number of AEs. BI standards as presented in “Analysis and Presentation of Adverse Event Data from Clinical Trials – Display Template” [BI-KMED-BDS-HTG-0041] (9) and [BI-KMED-BDS-HTG-0066] (10) will be applied.

The analysis of AEs will be based on the concept of treatment emergent AEs. That means that all AEs will be assigned to ‘screening’, ‘on treatment’ and ‘follow-up’ phases as defined in [Section 6.1](#). AEs will be analysed based on actual treatments, as defined in [Table 6.1: 1](#).

According to the clinical study protocol, adverse events of special interest (AESI) will be analysed:

Section 5.2.5.1.4 of the CTP: *The following are considered as AESIs:*

- Hepatic injury
A hepatic injury is defined by the following alterations of hepatic laboratory parameters:
 - o *An elevation of AST (aspartate transaminase) and/or ALT (alanine transaminase) ≥ 3 -fold ULN combined with an elevation of total bilirubin ≥ 2 -fold ULN measured in the same blood sample, or*
 - o *Aminotransferase (ALT, and/or AST) elevations ≥ 10 fold ULN*

According to ICH E3 (11), in addition to Deaths and Serious Adverse Events, ‘other significant’ AEs need to be listed in the clinical trial report. These will be any non-serious adverse event that led to an action taken with study drug (e.g. discontinuation or dose reduced or interrupted).

An overall summary of AEs will be presented.

The frequency of subjects with AEs will be summarised by treatment, primary system organ class (SOC) and preferred term (PT). Separate tables will be provided for subjects with serious AEs, for subjects with drug-related AEs, for subjects with drug-related serious adverse events and for subjects with AESIs. In addition, the frequency of subjects with AEs will be summarised by treatment, worst intensity, primary system organ class (SOC) and preferred term (PT).

The system organ classes will be sorted alphabetically, PTs will be sorted by frequency (within SOC).

In addition, frequencies of subjects with non-serious AEs that had an incidence of $> 5\%$ for at least one treatment will be summarised by treatment, primary SOC and PT.

7.8.2 Laboratory data

The analyses of laboratory data will be descriptive in nature and will be based on BI standards [BI-KMED-BDS-HTG-0042] (12).

Laboratory data will be analysed qualitatively via comparison of laboratory data to their reference ranges. Values outside the reference range as well as values defined as possibly clinically significant will be flagged in the data listings.

Clinically relevant findings in laboratory data will be reported as baseline conditions (at screening) or as AEs (during the trial) if judged clinically relevant by the investigator, and will be analysed as such.

It is the investigator's responsibility to decide whether a lab value is clinically significantly abnormal or not (at the RPM at the latest).

Descriptive statistics of laboratory data including change from baseline will be calculated by planned time point based on the worst value of the subject at that planned time point (or assigned to that planned time point).

7.8.3 Vital signs

For vital signs (blood pressure, pulse rate and body temperature), descriptive statistics including change from baseline will be calculated by treatment group and by planned time point based on the value of the subject that was originally assigned to the respective planned time point (unscheduled measurements will not be considered). Additionally, individual time profiles of body temperature will be provided, including unscheduled measurements using the actual time of measurement. In the listings the difference from baseline will also be displayed.

Clinically relevant findings will be reported as baseline conditions (at screening) or as AEs (during the trial) if judged clinically relevant by the investigator, and will be analysed as such.

7.8.4 ECG

Continuous safety ECG monitoring (by investigator)

Clinically relevant abnormal findings will be reported as adverse events.

No separate listing or analysis of continuous ECG monitoring will be prepared.

12-lead ECG

Abnormal findings will be reported as baseline conditions (at screening) or as AEs (during the trial) if judged clinically relevant by the investigator. All evaluations of ECG data will be based on the TS, except the exposure-response analyses, which are based on the ECGPCS.

Listing of individual data

For all quantitative endpoints, listings of individual data will be shown in Appendix 16.2. For QTcB and RR, only listings will be provided. Occurrences of notable findings will be flagged.

Comments regarding the ECGs will be listed.

Categorical endpoints

For the categorical endpoints, frequency tables will be provided.

For all subjects with any notable finding in ECG intervals, a separate listing will be created as end-of-text display (based on the same display template as in Appendix 16.2), and the corresponding time profiles will be shown.

Quantitative endpoints

Descriptive statistics (N, mean, SD, min, median, max) will be provided for the absolute values and changes from baseline over time of QTcF, QT, HR, PR and QRS. The time profiles of mean and SD for the changes from baseline on treatment will be displayed graphically by treatment. No totals will be provided.

Exposure-response assessment

For QTcF and HR changes from baseline, the relationship to the corresponding plasma concentrations (if applicable both for BI 706321 and BI 706062) will be analysed. For Part I, the relationship will be evaluated using figures and a random coefficient model.

For subjects in the ECGPCS, all time points with available ECG endpoints and valid time-matched drug plasma concentrations will be included. For a list of time points with scheduled ECG assessments and time-matched plasma concentrations as well as for definition of “time-matched”, refer to [Section 6.7](#). For the handling of missing values, see [Section 6.6](#).

The response variable will be the change from baseline in QTcF (Δ QTcF). The placebo subjects will be included in the analysis, setting their concentrations to zero.

As a first step for Part I, it is investigated if there is a potential delayed or accelerated (e.g. due to metabolites) effect of the drug on QTcF. A general visual impression will be provided by overlaying time profiles of plasma concentrations and QTcF changes from baseline (Δ QTcF). These figures will be generated for each subject (presented in the Statistical Appendix of the CTR), as well as for means per treatment group (presented in the End-of-Text part of the CTR).

For Part I, analysis will proceed like follows:

The relationship between BI 706321 plasma concentrations and QTcF changes from baseline will be investigated in an exploratory manner using a random coefficient model to estimate the difference in means between BI 706321 and placebo of QTcF change from baseline and its 90% confidence interval at the geometric mean of C_{max} after single dose and of $C_{max,ss}$ for each dose. Additionally, the estimated overall slope with its 90% confidence interval will be provided. The used random coefficient model is based on a white paper from Garnett et al. (13) with Δ QTcF as response variable, centered baseline QTc and plasma concentration as continuous covariates and treatment, time and day as fixed categorical effects, and a random intercept and slope for each subject. Restricted maximum likelihood estimation will be performed, and the Kenward-Roger method will be applied to adjust standard errors and estimate denominator degrees of freedom. For more details refer to [Section 10.1.4](#).

For visualization, a scatterplot of the BI 706321 plasma concentration against the following individual QTcF values will be provided: For each subject on active treatment and each time point, subtract the mean value of all individual observed Δ QTcF values from the placebo group for this time point from the individual observed Δ QTcF value for this subject and time point. This results in estimates for “individual $\Delta\Delta$ QTcF” values, which should only be used for plotting purposes. The corresponding regression line and its pointwise confidence bands as well as and the geometric mean of C_{max} and $C_{max,ss}$ for each dose will additionally be displayed in the plot.

The goodness of fit of the above model will be checked. The visual checks will include the inspection of concentration-QTcF quantile plots (13) and residual plots. In case of non-linearity or if there is evidence for a delayed effect, further models will be explored in order to better characterise the PK-ECG relationship.

All of the above described graphical and statistical analyses will be also performed for HR in place of QTcF, and if applicable for metabolite BI 706062 (both QTcF and HR) instead of the parent drug BI 706321.

Appropriateness of heart rate correction methods of QT interval

To evaluate the appropriateness of the heart rate correction methods, the slope of the relationship of QTcF interval versus RR interval will be estimated separately for off-drug values and active treatment, by applying the random coefficient model described in [Section 10.1.2](#) using the QTcF and RR variable values per time point. A scatterplot of QTcF vs RR including the overall regression lines will be included in the Statistical Appendix of the CTR.

Additionally, the slope of the relationship of log-transformed QT interval versus log-transformed RR interval will be estimated separately for off-drug values and active treatment, by applying a random coefficient model per single ECG.

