10.1.4 SAS code for ECG exposure-response analyses

```
PROC MIXED DATA=myDATA METHOD=REML;
  CLASS subject active(ref='0') [time day];
  MODEL ECGep = base conc active [time day] / NOINT CL ALPHA=0.1
  DDFM=KR; /* time is only included in case no baseline day is
  available*/
  RANDOM INT conc / TYPE=UN SUBJECT=subject;
  ESTIMATE 'Pred. value at conc. xx.xx' conc xx.xx active 1 -1 / CL
  ALPHA=0.1;
  ESTIMATE 'Intercept' conc 0 active 1 -1/CL ALPHA=0.1;
  ESTIMATE 'Slope estimate' conc 1 / CL ALPHA=0.1;
RUN;
```

Here ECGep is the QTcF change from baseline, base is the centered baseline value of ECGep (i.e. the baseline value minus the mean of the baseline values from all subjects), active is a dummy 0/1 variable indicating the active treatment (1=active, 0=placebo), time is a categorical variable indicating the time point, day is a categorical variable indicating the day, conc is the corresponding plasma concentration value of the drug, and xx.xx is the given concentration value (usually the value of the geometric mean C_{max} of a given treatment group). Note that the fixed effect time should be coded as the (planned) time of the day, i.e. as 24 hour clock time within the interval [0:00, 24:00) and not as the nominal time after first dose. That is, the time variable value for e.g. 08:00 on Day 1 should have the same value as for 08:00 on Day 2. The TYPE=UN option causes the two specified random coefficients to have a bivariate normal distribution. In case of convergence problems see [Section 10.1.5](#).

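### The delay check in SAP 7.8.4 overlays concentration on ΔQTcF without placebo correction, so a shift common to active and placebo subjects could move the apparent QTcF peak; overlaying ΔΔQTcF is a cheap improvement.

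*SAP*

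**What the plan says.** SAP 7.8.4 (Exposure-response assessment) describes a first step for Part I in which "it is investigated if there is a potential delayed or accelerated (e.g. due to metabolites) effect of the drug on QTcF". The tool is a figure: "A general visual impression will be provided by overlaying time profiles of plasma concentrations and QTcF changes from baseline". It is drawn for each subject, "as well as for means per treatment group (presented in the End-of-Text part of the CTR"). No placebo subtraction is stated for these overlays.

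The baseline behind ΔQTcF is set in SAP 6.7: "The baseline value of an ECG variable is defined as the mean of the ECG variable values prior to drug administration". Table 6.7: 1 places the baseline recordings at 1:30, 1:15 and 1:00 h before the Day 1 dose. There is no baseline day with matching clock times.

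SAP 7.8.4 does define a placebo-corrected quantity, but for a different figure. For the scatterplot against concentration, the instruction is to "subtract the mean value of all individual observed" placebo ΔQTcF values at the same time point from each active subject's value. The result is an individual ΔΔQTcF "which should only be used for plotting purposes".

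After the goodness-of-fit checks, which include concentration-QTcF quantile plots and residual plots, the section adds that in case of non-linearity or "if there is evidence for a delayed effect, further models will be explored". No numerical criterion for a delayed effect is given.

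**The concern.** A delay is judged by eye, by comparing when QTcF peaks with when concentration peaks. With a single early-morning baseline, every later ΔQTcF also contains whatever QTcF does with clock time, meals or study day in the absence of drug. The protocol's Part I flow chart puts lunch after the 4 h measurements and dinner at 10 h on Days 1 and 19. Median tmax,ss at 10 mg is 5 h, between the 4 h and 8 h triplicate ECGs, so the comparison that matters most for timing runs from fasted to fed.

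The SAP allows for such effects in the model. Time and day are fixed effects, and in SAP 10.1.4 "time is a categorical variable indicating the time point", coded as clock time. The overlay has no equivalent protection. The placebo-corrected values are used only in a scatterplot, which has no time axis and so cannot show a delay directly. What is at stake is the timing evidence: a shared afternoon rise could look like a delay, and a shared fall could hide one.

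**Working it through.** The plan states no threshold or shift, so there is no figure to reproduce. The check asks how large a shared shift would have to be.

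**Inputs**
- Effect at gMean Cmax,ss: slightly above 5 ms at 8 and 10 mg (Protocol 1.4.2.1.3); 5 ms is used.
- 10 mg steady state: Cmax,ss 39.9, C24,ss 18.6 nmol/L, AUCτ,ss 574 nmol·h/L, median tmax,ss 5 h (Protocol Table 1.2.1: 2).
- Single doses: 10 mg Cmax 11.5, C24 4.68; 2 mg Cmax 2.85, C24 1.27 nmol/L (same table).
- Group sizes: 9 active per dose, 12 pooled placebo (SAP 6.1).
- Assumed: an immediate linear effect with zero intercept; a linear rise to 5 h; after that either (a) a log-linear decline to 24 h, or (b) a biexponential decline with a 45 h terminal half-life, matched to Cmax, C24 and the reported AUC.

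**Shift that makes 8 h look as high as the peak**

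Slope = 5 / 39.9 = 0.1253 ms per nmol/L. Shift needed = slope × (Cmax − C at 8 h).

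| Case | C at 8 h, (a) | Shift (a) | C at 8 h, (b) | Shift (b) |
|---|---|---|---|---|
| 10 mg steady state | 39.9 × (18.6/39.9)^(3/19) = 35.37 | 0.57 ms | 24.9 | 1.88 ms |
| 10 mg single dose | 9.98 | 0.19 ms | 8.72 | 0.35 ms |
| 2 mg single dose | 2.51 | 0.04 ms | 2.01 | 0.11 ms |

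At 8 mg steady state the range is 0.49 to 1.33 ms, and at 5 mg 0.17 to 0.57 ms. At 2 mg steady state only (a) could be computed, giving about 0.06 ms. If the 5 ms is attached to the 8 mg Cmax,ss of 34.7, the slope is 0.144 and every shift is about 15% larger. No ECG is taken at 5 h. Measured from the 4 h concentration on the linear rise (35.6), the 10 mg steady-state gap to 8 h is smaller: 0.03 ms under (a) and 1.35 ms under (b).

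**Which shape fits the documents**

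Under (a) at 10 mg steady state, the AUC is 5 × (18.6 + 39.9)/2 + 19 × (39.9 − 18.6)/ln(39.9/18.6) = 146 + 530 ≈ 677, about 18% above the reported 574 nmol·h/L. Protocol 1.2.1 also calls the decline multiphasic. The upper end of the range is therefore closer to the reported data at this dose.

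**Effect of noise**

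The SD of ΔQTcF is not given; 3, 6 and 9 ms were assumed. Mean profiles at 1, 2, 4, 8, 12 and 24 h were simulated 100,000 times with no true delay, the 4 h concentration set at 0.98 × Cmax, and the shift added at 8 and 12 h. The table shows the chance that the mean profile peaks at 8 or 12 h, for 10 mg steady state (SD 3 / 6 / 9):

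| Shift | Uncorrected, (a) | Uncorrected, (b) |
|---|---|---|
| −1 ms | 0.14 / 0.25 / 0.29 | 0.02 / 0.12 / 0.18 |
| 0 | 0.40 / 0.41 / 0.40 | 0.11 / 0.23 / 0.27 |
| +1 ms | 0.71 / 0.59 / 0.52 | 0.34 / 0.38 / 0.38 |

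With placebo subtraction the chance no longer depends on the shift: 0.38 to 0.42 under (a), and 0.16 / 0.26 / 0.29 under (b). The cost is in the standard error: √(1/9 + 1/12) / √(1/9) = 0.441 / 0.333 = 1.32. At SD 6 ms it goes from 2.00 to 2.65 ms.

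**The case against.** The strongest reply is that the plan already contains the protection. Placebo is one of the treatment groups (SAP Table 6.1: 1), so its mean overlay and its mean change-from-baseline profile are both planned, and a shared drift can be seen by comparing panels. The overlay is described only as a visual impression, and the sentence on further models follows the quantile and residual plots from a model that includes placebo subjects, time and day. BI 706062 gets the same analyses if applicable, so a metabolite-driven effect does not rest on the parent-drug figure. The analysis is exploratory, and Protocol 7.2 plans no hypothesis tests.

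All of this stands, and it limits the point to the quality of one display. It does not remove the point. Comparing separate panels by eye is weaker than plotting the difference, and the subject-level overlays have no placebo reference.

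A reader might infer more: that a drift of about 1 ms is enough to create or hide a delay, or that the choice of model hangs on this figure. The documents support neither. They report no time-of-day QTcF shift of any size. Under the biexponential shape, 1 ms does not move the noise-free peak at 10 mg steady state, although 2 ms does. The overlay is not the only evidence for further models.

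Noise also limits what correction can achieve. With 9 subjects and no shift, a late peak still appears in roughly 10 to 45% of simulated profiles, and subtraction does not lower that.

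**Conclusion.** The point holds as a minor improvement. The overlay used to look for a delay is not placebo-corrected and would carry any shared time-of-day, meal or day effect. Whether such an effect exists in this setting is not documented. If it does, about 0.6 to 1.9 ms would make 8 h look as high as the peak at 10 mg steady state, and about 0.04 to 0.35 ms would do so after single doses. These figures rest on an immediate linear effect of 5 ms at the 10 mg Cmax,ss and on the two assumed PK shapes.

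It would be wrong to read this as bias in the planned estimates. The slope and the predicted differences at gMean Cmax and Cmax,ss come from a model that includes placebo subjects, time and day. Only the visual evidence on delay is affected.

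**What to change.** In SAP 7.8.4, add overlays of group-mean ΔΔQTcF (active minus the pooled placebo mean at the same planned time), with confidence intervals, on group-mean concentration. Make these the main display for the delay check and keep the ΔQTcF overlays as a supplement. Do the same for HR and, if applicable, BI 706062. If the Part I figures already exist, the new ones can be added as supplementary output.

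The cost is a little extra plotting and no new data. The standard error per time point rises by about 32%. The same pooled placebo mean enters every dose group, so chance error in it appears in all four profiles. The peak should therefore be read together with the intervals, not from the highest point alone.
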